## **5.2. Secondary Outcome Analysis**

All secondary outcomes will be analyzed as for a superiority designed trial and two-sided significance with alpha=5% and standard 95% CIs for the treatment differences in these outcomes between two groups will be calculated and presented. Secondary outcome analyses will be based on the mITT population unless specified.

The continuous outcome such as weight will be summarized using number of subjects (n), mean, standard deviation (SD), minimum, and maximum by treatment group, and will be analyzed by a GLMM model. Mean differences with 95% confidence intervals between two groups will be derived from the GLMM model.

All the secondary outcomes would be analyzed in the same tactics of primary outcome described above.

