1.2 Objectives

This randomized controlled trial aims to compare the efficacy of Baduanjin exercise to routine physical exercise in ADHD patients with Hyperactive-Impulsive Symptoms after three months of exercise and evaluate whether this effect will last for another three months.

The primary objective is to compare the Hyperactivity/Impulsivity change scores between two groups of The Swanson, Nolan, and Pelham Questionnaire (SNAP-IV) Rating Scale in 3th and 6th months after initiation. The secondary objective of this study is to evaluate the change in Scoring evaluation of the TCM symptoms after 3 months of treatment and 6 months of follow-up. In addition, the mediating effect of executive function measured by the CANTAB test and BRIEF2 scale will be calculated. Furthermore, we will determine whether these effects extend to other ADHD-related problems, including the sensory integration score, the Developmental Test of Visual Perception, and other behavioral problems.

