2.7 Participant timeline

Outcome measures are collected at enrolment, 3 months allocation, and 6 months post allocation. The flow of the trial is presented in Figure 1. A schematic diagram of enrolment, interventions, and assessments is described in Table 1.

TG: treatment group, CG: control group, SNAP-IV: The Swanson, Nolan, and Pelham Questionnaire

Figure 1 Flow diagram showing study design and subject allocation

Table 1 Enrolment, interventions, and assessments

| | STUDY PERIOD | | | |
|-------------|--------------|------------|-----------------|-----------|
| | Enrolment | Allocation | Post-allocation | Close-out |
| TIMEPOINT** | -2 Weeks | 0 | 3 months | 6 months |
| ENROLMENT: | | | | |

| | | | | |
|--|---|---|---|---|
| Eligibility screen | ✓ | | | |
| Informed consent | ✓ | | | |
| Allocation | | ✓ | | |
| INTERVENTIONS: | | | | |
| Baduanjin practice | ✓ | ✓ | ✓ | ✓ |
| routine physical exercise | ✓ | ✓ | ✓ | ✓ |
| ASSESSMENTS: | | | | |
| Primary Outcome: SNAP-IV clinician-rated Hyperactivity/Impulsivity score | ✓ | | ✓ | ✓ |
| Secondary Outcome: Scoring evaluation of the TCM symptoms(researcher rated) | ✓ | | ✓ | ✓ |
| Other outcome measures: | | | | |
| SNAP-IV parent/clinician-rated inattention and ODD score | ✓ | | ✓ | ✓ |
| WFIRS (parent completed) | ✓ | | ✓ | ✓ |
| CBCL (parent completed) | ✓ | | ✓ | ✓ |
| SDQ(parent and child completed) | ✓ | | ✓ | ✓ |
| CANTAB(child completed) | ✓ | | ✓ | ✓ |
| BRIEF-2 (parent completed) | ✓ | | ✓ | ✓ |
| DTVP-2(child completed) | ✓ | | ✓ | ✓ |
| Child Sensory Integration Checklist (parent completed) | ✓ | | ✓ | ✓ |

SNAP-IV: The Swanson, Nolan, and Pelham Questionnaire; TCM: Traditional Chinese Medicine; ODD: Oppositional Defiant Disorder; WFIRS: Weiss Functional Impairment Rating Scale; CBCL: Achenbach Child Behavior Checklist; SDQ: Strengths and Difficulties Questionnaire; CANTAB:

Cambridge neuropsychological test automated battery; BRIEF-2: Behavior Rating Inventory of Executive Function, Second Edition; DTVP-2: Visual Perception of children is measured by the Developmental Test of Visual Perception-2nd edition.

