2.15 Statistical methods

2.15.1 Statistical methods for primary and secondary outcomes

The primary outcome is a continuous variable: Hyperactivity/Impulsivity score change in the SNAP-IV scale. The primary analysis will be based on the intention-to-treat (ITT) population. The generalized linear model (GLM) will be used to test the difference 3 months after allocation between the groups. The estimated means and two-sided 95% confidence intervals (CI) will be derived. All secondary outcomes will be analyzed for a superiority-designed trial and two-sided significance with alpha=5% and standard 95% CIs for the treatment differences in these outcomes between the two treatment groups. Secondary outcome analyses will be based on the ITT population unless specified. SAS (version 9.4) will be used to perform all data analyses and generate the majority of data displays. STATA® (version 16.0) or SPSS, S-Plus, or R may also be used for data analyses and for generating statistical graphs. The other outcome measures will be calculated and presented with the same method of primary and secondary outcomes. Continuous variables will be summarized according to the number of subjects with non-missing data (n), mean, standard deviation (SD), median, minimum, maximum, and range interquartile (IQR). The confidence intervals will be reported on summaries of continuous effectiveness variables. Categorical variables will be summarized according to the absolute frequency and percentage of subjects (%) in each category level. The denominator for the percentages is the number of subjects in the treatment arm with data available unless noted otherwise.

Detailed information is displayed in the SAP.

2.15.2 Plans to give access to the complete protocol, participant-level data, and statistical code

The datasets used and analyzed during this trial can be granted access by the corresponding author and the safety monitoring board(DSMB) of CTU upon reasonable written request.

3 Oversight and monitoring

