### **2.2.2. Secondary outcomes**

(1) Hyperactivity/Impulsivity score change assessed by doctor version of SNAP-IV scale at 6th month.

Time Frame: Baseline, 6th month after initiation of intervention

Type: repeated measured continuous variable

(2) Hyperactivity/Impulsivity score changes assessed by parent version of SNAP-IV scale.

Time Frame: Baseline, 3th month and 6th month after initiation of intervention

Type: repeated measured continuous variable

(3) Changes of Scoring evaluation of the TCM symptoms.

Time Frame: Baseline, 3th month and 6th month after initiation of intervention

Type: repeated measured continuous variable

(4) Change scores of inattention and Oppositional Defiant Disorder (ODD) subscale assessed by doctor version of SNAP-IV scale.

Time Frame: Baseline, 3th month and 6th month after initiation of intervention

Type: repeated measured continuous variable

(5) Change scores of inattention and Oppositional Defiant Disorder (ODD) subscale score assessed by parent version of SNAP-IV scale.

Time Frame: Baseline, 3th month and 6th month after initiation of intervention

Type: repeated measured continuous variable

(6) The changes of Weiss Functional Impairment Rating Scale (WFIRS) score.

Time Frame: Baseline, 3th month and 6th month after initiation of intervention

Type: repeated measured continuous variable

(7) The changes of parent version of Achenbach Child Behavior Checklist (CBCL) score.

Time Frame: Baseline, 3th month and 6th month after initiation of intervention

Type: repeated measured continuous variable

(8) The changes of Child version of Achenbach Child Behavior Checklist (CBCL) score.

Time Frame: Baseline, 3th month and 6th month after initiation of intervention

Type: repeated measured continuous variable

(9) The changes of CANTAB test (neuropsychological tests) score.

Time Frame: Baseline, 3th month and 6th month after initiation of intervention

Type: repeated measured continuous variable

(10) The changes of BRIEF2 scale (ecological rating scale) score.

Time Frame: Baseline, 3th month and 6th month after initiation of intervention

Type: repeated measured continuous variable

(11) The changes of Visual Perception-2nd edition (DTVP-2) score.

Time Frame: Baseline, 3th month and 6th month after initiation of intervention

Type: repeated measured continuous variable

(12) The changes of Child Sensory Integration Checklist score.

Time Frame: Baseline, 3th month and 6th month after initiation of intervention

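### All 12 secondary outcomes are tested for superiority at 5% with no multiplicity control or exploratory label: about a 32–75% chance of at least one false positive, 16–50% in Baduanjin's favour

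*SAP*

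**What the plan says.** **Testing rule.** SAP 5.2: "All secondary outcomes will be analyzed as for a superiority designed trial and two-sided significance with alpha=5" (per cent). Protocol 2.15.1: "All secondary outcomes will be analyzed for a superiority-designed trial and two-sided significance with alpha=5" (per cent). Neither document contains an adjustment, a testing order, a gate after the primary, or an exploratory label.

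**Number of outcomes.** SAP 2.2.2 numbers 12 secondary outcomes. Item (1) is "Hyperactivity/Impulsivity score change assessed by doctor version of SNAP-IV scale at 6th month", a single visit. Items (2) to (12) have the time frame "Baseline, 3th month and 6th month after initiation of intervention", so two follow-up visits each. Items (4) and (5) each hold two subscales, for example "Change scores of inattention and Oppositional Defiant Disorder (ODD) subscale assessed by doctor version of SNAP-IV scale".

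**Extra analyses.** SAP 5.2 adds: "All the secondary outcomes would be analyzed in the same tactics of primary outcome described above". The primary-outcome section contains the main mixed model (5.1.1) and the per-protocol (5.1.2), covariate-adjusted (5.1.3) and subgroup (5.1.4) analyses. The plan does not say which of these carry over.

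**Hierarchy.** Protocol 1.2: "The secondary objective of this study is to evaluate the change in Scoring evaluation of the TCM symptoms". Table 1 in Protocol 2.7 likewise has one line marked "Secondary Outcome: Scoring evaluation of the TCM symptoms(researcher rated" and puts the remaining scales under a heading for other outcome measures. Protocol 2.6.2, however, numbers seven groups of scales as secondary, and SAP 2.2.2 lists 12.

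**The concern.** A 5% test limits the error of one comparison. Here the same 5% is given to every secondary comparison, and the plan describes the result of each as a superiority test. With this many comparisons, one or more nominally significant results are to be expected even if Baduanjin and routine exercise have the same effect. Nothing in the plan tells a reader which secondary result, if any, was meant to be confirmatory, or that the others should be read as descriptive. At stake is the reliability of any superiority statement based on a secondary score. The conflict over which outcomes are secondary makes this worse, because the size of the family depends on which section is followed.

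**Working it through.** **1. The plan's own figure.** The documents give no family-wise error rate. Their only error-rate calculation is the sample size in SAP 3.6: difference 3.1, SD 5.8, two-sided 5%, power 80%. The normal approximation gives 55 per arm. The t-test gives 56, with power 80.05%, which matches the plan. Allowing for 5% drop-out, 56 / 0.95 rounds up to 59 per arm, or 118, and 120 is the next multiple of the block size of 4. The figure reproduces, and it uses the 5% on one primary test.

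**2. Count of secondary tests** (SAP 2.2.2, one score per instrument):

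- Item (1), month 6 only: 1
- Items (2) and (3), two visits each: 2 + 2 = 4
- Items (4) and (5), two subscales at two visits: 4 + 4 = 8
- Items (6) to (12), seven items at two visits: 7 × 2 = 14
- Total: 1 + 4 + 8 + 14 = **27**

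With each numbered item as one test per visit, the count is 1 + 11 × 2 = 23. The shell of SAP Table 3 has 11 measures at two visits, so 22 p-values, of which one is the primary: 21 secondary. That shell omits TCM, CANTAB and BRIEF-2.

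**3. Expected false positives when no outcome differs.** 27 × 0.05 = 1.35, of which 27 × 0.025 = 0.675 favour Baduanjin. These hold whatever the correlation.

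**4. Chance of at least one, independent tests.**

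- Either direction: 1 − 0.95^27 = 75.0%
- Favouring Baduanjin: 1 − 0.975^27 = 49.5%

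**5. Chance of at least one, correlated tests.** The documents give no correlations between outcomes. Equal correlation r is therefore assumed, with 100,000 simulated sets of normal test statistics for each value.

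| r (assumed) | 27 tests: either direction | 27 tests: favouring Baduanjin | 21 tests: either direction | 21 tests: favouring Baduanjin |
|---|---|---|---|---|
| 0 (exact) | 75.0% | 49.5% | 65.9% | 41.2% |
| 0.3 | 63.0% | 33.2% | 55.1% | 28.8% |
| 0.5 | 48.1% | 24.3% | 43.0% | 21.6% |
| 0.7 | 32.5% | 16.3% | 29.4% | 14.8% |

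The 23-test count lies between the two. At r = 0.7 it gives 30.4% and 15.1%.

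**6. The primary.** SAP 4.1 states one hypothesis, on one score at month 3, and SAP 5.1.1 names one primary analysis. Its error rate stays at 5% (2.5% in Baduanjin's favour).

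**The case against.** The best defence is that the primary conclusion is protected, that the word secondary already signals a lower rank, and that no sentence lets a significant secondary result replace a null primary. The first and third parts stand. The second does not settle the matter, because the plan itself attaches superiority and a 5% significance level to every secondary outcome.

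Four stronger readings are tempting, and the documents do not support them.

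- **A false finding for Baduanjin is likely.** The higher percentages count errors in both directions. In Baduanjin's favour the 27 tests give 16–33% for r from 0.7 to 0.3, and about 50% only under independence, which is unrealistic for scales rating the same child twice. The chance passes one half for these 27 outcome-visit comparisons only if the subgroup analyses are also read as tests. In 600 simulated null trials per setting, with an assumed 75% in the per-protocol set and assumed subgroup sizes, it was 72–95%.
- **The SAP promoted minor outcomes.** Protocol 2.6.2 already lists seven groups as secondary, and Protocol 2.15.1 already applies the 5% rule. The conflict lies within the protocol.
- **There are 123 planned tests, or 492 with repeats.** The first count takes every outcome score in SAP section 7, which is a variable list that also holds administrative fields. No passage says each score is tested. The second multiplies by four on one reading of the sentence about using the same tactics. Sections 5.1.2 to 5.1.4 are titled for the primary outcome, the per-protocol set is called supportive, and SAP 5.2 defaults to the mITT population.
- **Parent and child ratings make the error rate worse.** Whether the rater knows the arm is a question of bias, separate from multiplicity.

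**Conclusion.** The point holds for the secondary outcomes only. All 12 are tested for superiority at two-sided 5%, 11 of them at two visits and item (1) at month 6 only, with nothing to control or qualify the family of tests. On a count of 27, the chance of at least one false-positive secondary result is about 32–75% in either direction and 16–50% in Baduanjin's favour. These figures rest on no true difference in any outcome, one score per instrument, and an assumed common correlation between 0.7 and 0. Narrower counts of 21 or 23 tests lower them by a few points and do not change the conclusion. Subgroup analyses are not included. The primary test keeps its 5%. A reader should not infer that the trial's main conclusion is unreliable, or that a false result for Baduanjin is more likely than not.

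**What to change.** In SAP 5.2 and Protocol 2.15.1:

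1. Report the secondary outcomes as estimates with 95% CIs, labelled exploratory, with no superiority or significance claim.
2. If one confirmatory secondary is wanted, name the blinded TCM total score change at month 3, the time point in Protocol 2.6.2. Test it at two-sided 5% only if the primary is significant. The two tests together then stay within 5%.
3. Replace the sentence about using the same tactics rather than delete it, since it is what gives the secondary outcomes the model specification of 5.1.1. The new sentence should say that secondary outcomes use the mixed model of 5.1.1, and that per-protocol, adjusted and subgroup analyses apply to the primary outcome or are exploratory if repeated for secondary outcomes.
4. Reconcile Protocol 1.2 and Table 1, which reserve the secondary label for TCM, with Protocol 2.6.2 and SAP 2.2.2.
5. State the status of clinician-rated Hyperactivity/Impulsivity at month 6. Protocol 1.2 puts it in the primary objective, and SAP 2.2.2 makes it secondary.

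The cost is a few sentences. Data, visits and sample size do not change. The sponsor gives up unadjusted superiority claims on the other secondary scores.

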### **5.2.1. Handling of Missing data**

Missing baseline covariates will be imputed using simple imputation methods in the covariate adjusted analysis based on the covariate distributions, should the missing values for a particular covariate be less than 5%. For a continuous variable, missing values will be imputed from random values from a normal distribution with mean and SD calculated from the available sample. For a categorical variable, missing values will be imputed from random values from a uniform distribution with probabilities P1,

P2, ..., and Pk from the sample. The seed to be used is 20211215.

## 6.General Considerations for Data Analyses

SAS (version 9.4) will be used to perform all data analyses and generate majority of data displays. STATA® (version 16.0) or R may also be used for some data analyses and generating statistical graphs.

### 6.1. Other Data Summaries

Continuous variables will be summarized according to number of subjects without missing data (n), mean, standard deviation (SD), median range interquartile (IQR), minimum, and maximum. The confidence intervals will be reported on summaries of continuous effectiveness variables. Categorical variables will be summarized according to the absolute frequency and percentage of subjects (%) by category levels. The denominator for the percentages is the number of subjects in the treatment arm with data available, unless noted otherwise. Effect size ( $\eta^2$ , eta-squared) would be estimated by SAS by PROC marco %effect\_size or by R software with effectsize package.

### 6.2. Graphical/Table Displays

Mean values for some continuous outcomes by treatment and visit will be plotted.

Table 1A Baseline characteristics of patients

mITT Population

Variable	Statistics	Treatment A (N=)	Treatment B (N=)
Age at baseline (year)	Mean(SD)		
Height(cm)	Mean(SD)		
Weight(kg)	Mean(SD)		

Variable	Statistics	Treatment A (N=)	Treatment B (N=)
Using drug	Yes		
	No		
Gender	Female		
	Male		
SNAP scale score-INA-Doctor	Mean(SD)		
SNAP scale score-HYP-Doctor	Mean(SD)		
SNAP scale score-ODD-Doctor	Mean(SD)		
SNAP scale score -INA -Parents	Mean(SD)		
SNAP scale score-HYP-Parents	Mean(SD)		
SNAP scale score-ODD-Parents	Mean(SD)		

Table 2: Summary statistics of primary and secondary outcomes: changes from baseline

Measurements	Visit	Statistics	Treatment A (N=)	Treatment B (N=)
SNAP scale score-INA-Doctor	3 months	n		
		Mean		
		SD		
		Minimum		
		Median		
		Maximum		
	6 months	n		
		Mean		
		SD		
		Minimum		
		Median		
		Maximum		
SNAP scale score-HYP-Doctor	3 months	n		
		Mean		

Measurements	Visit	Statistics	Treatment A (N=)	Treatment B (N=)
		SD		
		Minimum		
		Median		
		Maximum		
	6 months	n		
		Mean		
		SD		
		Minimum		
		Median		
		Maximum		
SNAP scale score- ODD-Doctor	3 months	n		
		Mean		
		SD		
		Minimum		
		Median		
		Maximum		
	6 months	n		
		Mean		
		SD		
		Minimum		
		Median		
		Maximum		
SNAP scale score - INA -Parents	3 months	n		
		Mean		
		SD		
		Minimum		
		Median		
		Maximum		

Measurements	Visit	Statistics	Treatment A (N=)	Treatment B (N=)
	6 months	n		
		Mean		
		SD		
		Minimum		
		Median		
		Maximum		
SNAP scale score- HYP-Parents	3 months	n		
		Mean		
		SD		
		Minimum		
		Median		
		Maximum		
	6 months	n		
		Mean		
		SD		
		Minimum		
		Median		
		Maximum		
SNAP scale score- ODD-Parents	3 months	n		
		Mean		
		SD		
		Minimum		
		Median		
		Maximum		
	6 months	n		
		Mean		
		SD		
		Minimum		

Measurements	Visit	Statistics	Treatment A (N=)	Treatment B (N=)
		Median		
		Maximum		
Parent version of Achenbach Child Behavior Checklist (CBCL)	3 months	n		
		Mean		
		SD		
		Minimum		
		Median		
		Maximum		
	6 months	n		
		Mean		
		SD		
		Minimum		
		Median		
		Maximum		
Self-rated Strengths and Difficulties Questionnaire (SDQ)	3 months	n		
		Mean		
		SD		
		Minimum		
		Median		
		Maximum		
	6 months	n		
		Mean		
		SD		
		Minimum		
		Median		

Measurements	Visit	Statistics	Treatment A (N=)	Treatment B (N=)
		Maximum		
Weiss Functional Impairment Rating Scale (WFIRS)	3 months	n		
		Mean		
		SD		
		Minimum		
		Median		
		Maximum		
	6 months	n		
		Mean		
		SD		
		Minimum		
		Median		
		Maximum		
Visual Perception-2nd edition (DTVP-2)	3 months	n		
		Mean		
		SD		
		Minimum		
		Median		
		Maximum		
	6 months	n		
		Mean		
		SD		
		Minimum		
		Median		
		Maximum		
Child Sensory Integration Checklist	3 months	n		

Measurements	Visit	Statistics	Treatment A (N=)	Treatment B (N=)
		Mean		
		SD		
		Minimum		
		Median		
		Maximum		
	6 months	n		
		Mean		
		SD		
		Minimum		
		Median		
		Maximum		

Table 3.: Summary of mixed model analysis of primary and secondary outcomes

Primary and secondary outcomes	Visit	n,mean (SD)		Mixed model analysis	
		Treatment A (N=306)	Treatment B (N=306)	Difference (95%CI)	p-value
SNAP scale score-INA-Doctor	3 months				
	6 months				
SNAP scale score-HYP-Doctor	3 months				
	6 months				
SNAP scale score-ODD-Doctor	3 months				
	6 months				
SNAP scale score -INA -Parents	3 months				
	6 months				
SNAP scale score-HYP-Parents	3 months				
	6 months				
SNAP scale score-ODD-Parents	3 months				
	6 months				

		n,mean (SD)		Mixed model analysis	
Primary and secondary outcomes	Visit	Treatment A (N=306)	Treatment B (N=306)	Difference (95%CI)	p-value
Parent version of Achenbach Child Behavior Checklist (CBCL)	3 months				
	6 months				
Self-rated Strengths and Difficulties Questionnaire (SDQ)	3 months				
	6 months				
Weiss Functional Impairment Rating Scale (WFIRS)	3 months				
	6 months				
Visual Perception-2nd edition (DTVP-2)	3 months				
	6 months				
Child Sensory Integration Checklist	3 months				
	6 months				

Additional tables would be generated if more analysis were conducted.

## 7. Study variable list

Variable	Type
name	categorical
randomid	categorical
clinicalid	categorical
counselid	categorical
method	categorical
informaconsent	categorical
startdate	date
enddate	date
signature	categorical
inclusion1	categorical

inclusion2	categorical
inclusion3	categorical
inclusion4	categorical
inclusion5	categorical
inclusion6	categorical
inclusion7	categorical
inclusion8	categorical
inclusion9	categorical
exclusion1	categorical
exclusion2	categorical
exclusion3	categorical
exclusion4	categorical
exclusion5	categorical
exclusion6	categorical
exclusion7	categorical
exclusion8	categorical
firstcomplete	categorical
birthday	date
fathertel	categorical
mothertel	categorical
length	continuous
weight	continuous
peclass	continuous
oxtime	continuous
ropeskipping	continuous

slowrunning	continuous
quickrunning	continuous
pingpong	continuous
badminton	continuous
basketball	continuous
football	continuous
dancing	continuous
taekwondo	continuous
wushu	continuous
bicycle	continuous
otherpe	categorical
medicalusage	categorical
medicalusagetime	continuous
TotalIQ	continuous
languageunderstanding	continuous
Preconception	continuous
remember	continuous
processspeed	continuous
DSNAP_INA	continuous
DSNAP_HYP	continuous
DSNAP_ODD	continuous
PSNAP_INA	continuous
PSNAP_HYP	continuous
PSNAP_ODD	continuous
DTVPGVP	continuous
DTVPMRP	continuous
DTVPVMI	continuous
PSDQmotion	continuous
PSDQbehavior	continuous
PSDQhyperactivity	continuous
PSDQcompany	continuous
PSDQsocial	continuous
PSDQhardrelationT	continuous
CSDQmotion	continuous
CSDQbehavior	continuous
CSDQhyperactivity	continuous
CSDQcompany	continuous
CSDQsocial	continuous
CSDQhardrelationT	continuous
Gantong1	continuous
Gantong2	continuous

Gantong3	continuous
Gantong4	continuous
Gantong5	continuous
Gantong6	continuous
Gantong7	continuous
Gantong8	continuous
Gantong9	continuous
CBCL_1	continuous
CBCL_2	continuous
CBCL_3	continuous
CBCL_4	continuous
CBCL_5	continuous
CBCL_6	continuous
CBCL_7	continuous
CBCL_8	continuous
CBCL_9	continuous
WEISSfamily	continuous
WEISSstudyschool	continuous
WEISSlifeskill	continuous
WEISSself	continuous
WEISSsocial	continuous
WEISSadventure	continuous
inhibitT	continuous
Self-monitor T	continuous
Shift T	continuous
Emotional Control T	continuous
Initiate T	continuous
Working memory T	continuous
Plan/Organize T	continuous
Task-monitor T	continuous
Organization of materials T	continuous
BRI T	continuous
ERI T	continuous
CRI T	continuous
GEC T	continuous
TCM_shehong	continuous
TCM_shetai	continuous
TCM_mai	continuous
TCM_total	continuous
testdate	date
complete	categorical

whostop	categorical
otherstop	categorical
stopreason	categorical
otherstopreason	categorical
AE	categorical
AEdetail	categorical
ADeal	categorical
usemedicine	categorical
usemedicinedose	continuous
otherusemedicinedose	categorical
TotalIQ_3m	continuous
languageunderstanding_3m	continuous
Preconception_3m	continuous
remember_3m	continuous
processspeed_3m	continuous
DSNAP_INA_3m	continuous
DSNAP_HYP_3m	continuous
DSNAP_ODD_3m	continuous
PSNAP_INA_3m	continuous
PSNAP_HYP_3m	continuous
PSNAP_ODD_3m	continuous
DTVPGVP_3m	continuous
DTVPMRP_3m	continuous
DTVPVMI_3m	continuous
PSDQmotion_3m	continuous
PSDQbehavior_3m	continuous
PSDQhyperactivity_3m	continuous
PSDQcompany_3m	continuous
PSDQsocial_3m	continuous
PSDQhardrelationT_3m	continuous
CSDQmotion_3m	continuous
CSDQbehavior_3m	continuous
CSDQhyperactivity_3m	continuous
CSDQcompany_3m	continuous

CSDQsocial_3m	continuous
CSDQhardrelationT_3m	continuous
Gantong1_3m	continuous
Gantong2_3m	continuous
Gantong3_3m	continuous
Gantong4_3m	continuous
Gantong5_3m	continuous
Gantong6_3m	continuous
Gantong7_3m	continuous
Gantong8_3m	continuous
Gantong9_3m	continuous
CBCL_1_3m	continuous
CBCL_2_3m	continuous
CBCL_3_3m	continuous
CBCL_4_3m	continuous
CBCL_5_3m	continuous
CBCL_6_3m	continuous
CBCL_7_3m	continuous
CBCL_8_3m	continuous
CBCL_9_3m	continuous
WEISSfamily_3m	continuous
WEISSstudyschool_3m	continuous
WEISSlifeskill_3m	continuous
WEISSself_3m	continuous
WEISSsocial_3m	continuous
WEISSadventure_3m	continuous
inhibitT_3m	continuous
Self-monitor T_3m	continuous
Shift T_3m	continuous
Emotional Control T_3m	continuous
Initiate T_3m	continuous
Working memory T_3m	continuous
Plan/Organize T_3m	continuous
Task-monitor T_3m	continuous
Organization of materials T_3m	continuous
BRI T_3m	continuous
ERI T_3m	continuous
CRI T_3m	continuous
GEC T_3m	continuous
TCM_shehong_3m	continuous
TCM_shetai_3m	continuous
TCM_mai_3m	continuous

TCM_total_3m	continuous
testdate	date
complete	categorical
whostop	categorical
otherstop	categorical
stopreason	categorical
otherstopreason	categorical
AE	categorical
AEdetail	categorical
AEdetail	categorical
usemedicine	categorical
usemedicinedose	continuous
otherusemedicinedose	categorical
TotalIQ_6m	continuous
languageunderstanding_6m	continuous
Preconception_6m	continuous
remember_6m	continuous
processspeed_6m	continuous
DSNAP_INA_6m	continuous
DSNAP_HYP_6m	continuous
DSNAP_ODD_6m	continuous
PSNAP_INA_6m	continuous
PSNAP_HYP_6m	continuous
PSNAP_ODD_6m	continuous
DTVPGVP_6m	continuous
DTVPMRP_6m	continuous
DTVPVMI_6m	continuous
PSDQmotion_6m	continuous
PSDQbehavior_6m	continuous
PSDQhyperactivity_6m	continuous
PSDQcompany_6m	continuous
PSDQsocial_6m	continuous
PSDQhardrelationT_6m	continuous

CSDQmotion_6m	continuous
CSDQbehavior_6m	continuous
CSDQhyperactivity_6m	continuous
CSDQcompany_6m	continuous
CSDQsocial_6m	continuous
CSDQhardrelationT_6m	continuous
Gantong1_6m	continuous
Gantong2_6m	continuous
Gantong3_6m	continuous
Gantong4_6m	continuous
Gantong5_6m	continuous
Gantong6_6m	continuous
Gantong7_6m	continuous
Gantong8_6m	continuous
Gantong9_6m	continuous
CBCL_1_6m	continuous
CBCL_2_6m	continuous
CBCL_3_6m	continuous
CBCL_4_6m	continuous
CBCL_5_6m	continuous
CBCL_6_6m	continuous
CBCL_7_6m	continuous
CBCL_8_6m	continuous
CBCL_9_6m	continuous
WEISSfamily_6m	continuous
WEISSstudyschool_6m	continuous
WEISSlifeskill_6m	continuous
WEISSself_6m	continuous
WEISSsocial_6m	continuous
WEISSadventure_6m	continuous
inhibitT_6m	continuous
Self-monitor T_6m	continuous
Shift T_6m	continuous
Emotional Control T_6m	continuous
Initiate T_6m	continuous
Working memory T_6m	continuous
Plan/Organize T_6m	continuous
Task-monitor T_6m	continuous
Organization of materials T_6m	continuous
BRI T_6m	continuous
ERI T_6m	continuous
CRI T_6m	continuous

GEC T_6m	continuous
TCM_shehong_6m	continuous
TCM_shetai_6m	continuous
TCM_mai_6m	continuous
TCM_total_6m	continuous

